03	0074	24-Aug-2021	Updated principal investigators on page 1; clarified conduct physical exam versus physical questionnaire: when each occurs (Table 3, Appendix F) and what is included in each (Section 4.1 and Section 4.6). Updated Appendix L with risk analysis information from RMF1018. Revised angiographic core lab to "TBD".				
A	0090	22-Sep-2021	Released document to alpha revision level; updated angiographic core lab information from TBD to Yale University. Clarified sheath size as 6Fr or larger. Rounded the drug content in Table 1 to whole numbers. Added angiographic core lab technician worksheet and collection instructions to Apnedix I. Removed Appendices J and K (IVUS and OCT Core Lab Guidelines); renumbered remaining appendices.				

PROTOCOL SUMMARY

	Τ						
Investigational Device	CVT Everolimus-coated Percutaneous Transluminal Coronary Angioplasty (PTCA) Catheter						
Study Objective	To assess the safety and inhibition of restenosis of the CVT Everolimus- coated PTCA Catheter in the treatment of subjects presenting in-stent restenotic lesions in native coronary arteries.						
Study Design	Prospective, multi-center, open, single arm study enrolling subjects with visually estimated nominal vessel diameter $\geq 2.0 \text{ mm}$ and $\leq 3.5 \text{ mm}$ and lesion length $\leq 24 \text{ mm}$ receiving up to two (2) CVT Everolimus CVT EVE-PTCA Catheters. Angiographic follow up, in combination with with either Intravascular Ultrasound (IVUS) or Optical Coherence Tomography (OCT), follow-up, will be carried out in a subset of 25 patients at 180 days following the index procedure.						
Patient enrollment	A total of 50 subjects will be enrolled						
Number of Sites	Up to fifteen (15) clinical sites in Europe						
Primary Safety Endpoint	Freedom from target lesion failure (TLF) rate at 6 months post-index procedure, defined as a composite rate of cardiovascular death, target vessel myocardial infarction and clinically-driven target lesion revascularization (TLR).						
Primary Effectiveness Endpoint	In-stent late lumen loss (LLL) at 180 days post-procedure.						
Other Clinical Endpoints	 Target lesion failure (TLF) at 30 days, 1, 2 and 3 years post-procedure, defined as a composite rate of cardiovascular death, target vessel myocardial infarction and clinically-driven target lesion revascularization (TLR). Target vessel failure (TVF) at 30 days, 180 days, and 1, 2 and 3 years post-procedure, defined as a composite rate of cardiovascular death, target vessel myocardial infarction, and target vessel revascularization (TVR). Clinically-driven target lesion revascularization (TLR) at 1, 2 and 3 years post-procedure. Clinically-driven target vessel revascularization (TVR) at 180 days and 1, 2 and 3 years post-procedure. Rate of vascular access site complication, defined as the combined rate of hematoma, AV fistula or a pseudoaneurysm that required intervention, such as surgical repair or transfusion, prolonged hospital stay or required a new hospital admission. Lesion success (per device), defined as achievement of a final in-lesion residual diameter stenosis of <30% (by QCA), using any device after wire 						

	passage through the lesion. Pre- and post-dilatation of the lesion with a
	non-study device is considered part of assigned device treatment.
	• Technical success (per device), defined as achievement of a final in-lesion residual diameter stenosis of <30% (by QCA), using the CVT Everolimus-coated PTCA Catheter without a device malfunction after wire passage through the lesion. Pre- and post-dilatation are considered part of assigned device treatment.
	• Clinical success (per subject) defined as technical success without the occurrence of major adverse cardiac events during the procedure.
	• Procedural success (per subject) defined as lesion success without the occurrence of major adverse cardiac events during the procedure.
Angiographic, IVUS	Angiographic endpoints (subset of 25 subjects):
and OCT Endpoints	• In-segment LLL at 180 days
	• In-stent and in-segment % diameter stenosis (%DS) at 180 days
	• In-stent and in-segment angiographic binary restenosis (ABR) rate at 180 days
	IVUS endpoint (subset of 15 subjects):
	• In-stent % volume obstruction (%VO) at 180 days
	OCT endpoints (subset of 10 subjects):
	• % of stent strut coverage at 180 days
Subject	Subjects with documented in-stent restenosis in native coronary arteries.
Population	
Treatment Strategy	• Treatment of a single in-stent restenosis coronary artery lesion with up to two (2) CVT Everolimus-coated PTCA Catheters.
	• Target lesion must be treated after confirmation that all inclusion criteria are met and in absence of any exclusion criteria.
	• Pre-dilation of the target lesion is mandatory.
	• Treatment of the target lesion measuring ≤24 mm in length by visual estimation in a vessel of visually estimated diameter ≥2.0mm and ≤3.5mm.
	• Recommendation is to select a CVT EVE- PTCA Catheter with balloon length that allows for coverage of the targeted lesion plus approximately 2 mm additional coverage, by visual estimate, on each side of the lesion while not allowing the balloon length extend beyond the edges of the stent.
	• All subjects will be maintained on their routine therapeutic anticoagulation treatment or, in the absence of pre-existing treatment,

	• All subjects will undergo clinical examination at 6- and 12-months post- procedure and then will be contacted by phone at 24 and 36 months post-procedure to answer a health status questionnaire.
	• A subset of subjects will complete post-procedure angiography (n=25), with IVUS (n=15) or OCT (n=10) target vessel assessment, in order to compare with the angiographic, IVUS or OCT data obtained at the 6 month follow-up timepoint.
Inclusion Criteria	Study subjects must fulfill the following criteria:
	1. Subject must be at least 18 years of age.
	2. Subject or his/her legally authorized representative provides written informed consent prior to any clinical investigation related procedure, as approved by the appropriate Ethics Committee of the respective clinical site.
	3. Subject must agree to undergo all clinical investigation plan-required follow-up visits, angiograms, IVUS/OCT and examinations.
	Angiographic Inclusion Criteria
	 Target lesion must be located within a stent (bare metal or drug eluting) placed in a native epicardial coronary vessel with visually estimated nominal vessel diameter of ≥2.0mm and ≤3.5mm.
	2. Target lesion must measure ≤ 24 mm in length by visual estimation.
	 The target lesion must be with a visually estimated stenosis of ≥50% and < 100% with a TIMI flow of ≥1.
	 Non-clinical investigation, percutaneous intervention for lesions in a non-target vessel is allowed if done ≥90 days prior to or planned to be done 6 months after the index procedure.
	5. Non-clinical investigation, percutaneous intervention for lesions in the target vessel is allowed if planned to be done 6 months after the index procedure.
Exclusion Criteria	Subject with any of the following should be excluded:
	 Subject with known diagnosis of acute myocardial infarction (AMI) within 30 days preceding the index procedure and CK-MB or troponin have not returned within normal limits at the time of procedure.
	2. The subject is currently experiencing clinical symptoms consistent with AMI.
	3. Subject has current unstable arrhythmia.
	4. Subject has a known left ventricular ejection fraction (LVEF) <25%.
	5. Subject has a known hypersensitivity or contraindication to aspirin, both heparin and bivalirudin, both clopidogrel and ticlopidine and structurally related compounds, everolimus, or contrast sensitivity that cannot be adequately pre-medicated.
	 6. Subject has known renal insufficiency (e.g., serum creatinine > 2.5 mg/dL, (i.e. 221 μmol/L) within 7 days prior to index procedure or creatinine clearance <30mL/min or subject is on dialysis.
	7. Subject has a history of bleeding diathesis or coagulopathy or will

	refuse blood transfusions.
	8. Subject has had a cerebrovascular accident (CVA) or transient ischemic
	neurological attack (TIA) within the past six months.
	9. Subject has other medical illness (e.g., cancer or congestive heart
	failure) or known history of substance abuse (alcohol, cocaine, heroin
	etc.) that may cause non-compliance with the clinical investigation
	expectancy (i.e., less than one year).
	10. Subject is already participating in another clinical investigation that has not yet reached its primary endpoint.
	11. Subject is not, in the opinion of the investigator, an acceptable candidate to participate in the study.
	12. In-stent lesions for stent are located within an arterial or saphenous vein graft or stent used to treat a previous ISR.
	13. The target vessel contains visible thrombus.
	14. Pregnant or lactating females.
Planned Schedule:	• First subject enrolled: 2021
	• Last subject enrolled: 2022
	• Last subject last contact: 2025

1. STUDY OVERVIEW AND RATIONALE

1.1 Study Overview

The CVT-ISR study is a prospective, multi-center, open, single arm study which will include fifty (50) subjects at up to fifteen (15) sites in Europe and will evaluate the clinical safety and efficacy of an everolimus-coated percutaneous transluminal coronary angioplasty (PTCA) catheter for the treatment of in-stent restenosis (ISR) in native coronary lesions previously treated with drug-eluting stent (DES) or bare-metal stent (BMS).

Study enrollment will be offered to all subjects who are suitable candidates for balloon PTCA to correct in-stent restenosis lesions in native coronary arteries. Subjects who fail to match the inclusion criteria or who present with any of the exclusion criteria should not be included into this study.

To comply with regulatory requirements, subjects will be required to give written informed consent prior to their participation in the study.

1.2 Background and Literature Review

Stenting has been shown to be a safe and effective treatment of de novo lesions in native coronary arteries through conduct of numerous studies, with first bare-metal stents (BMS)¹⁻⁹ supplanted by drug-eluting stents (DES).¹⁰⁻¹⁸

Notwithstanding a successful procedure, coronary stents can fail to conserve vessel patency due to either in-stent restenosis (ISR) or stent thrombosis (ST),¹⁹ a relatively rare but serious complication that can cause a large non-fatal myocardial infarction (MI), or sudden death.²⁰ ISR, defined as the gradual re-narrowing of a stented coronary artery lesion due to arterial damage with subsequent neointimal tissue proliferation,²¹ remains a serious concern as a late stent implant complication. It usually presents as acute coronary syndrome in approximately 70 percent of patients but also can present as acute MI in approximately 10 percent of patients.²²

The incidence of ISR partly depends on type of stent originally implanted. BMS are becoming less commonly used in routine practice²³ and DES drastically reduce ISR observed with BMS. Overall, rates of ISR drop under 10 percent²³ with DES whereas rates range from 17 and 41 percent with BMS.²⁵ However, regardless of the lower ISR rate observed, in the field of interventional cardiology, ISR of DES remains a major clinical challenge.^{26, 27}

Various therapies intended to reduce the rate of ISR have been tested in clinical investigations and in clinical practice. As a first line of treatment, medication (antiplatelet agents, oral sirolimus) did not provide any clinical benefit.^{28, 29, 30}

Coronary surgery may be considered in patients with recalcitrant ISR, who are deemed to not be candidates for percutaneous intervention, particularly in those with a diffuse ISR pattern or associated or significant disease in other major vessels.³¹

Regarding medical devices, debulking techniques (including rotational atherectomy and laser) and cutting balloons have proved to be ineffective for the treatment of ISR.^{32, 33}

Multiple studies comparing techniques of plain old balloon angioplasty (POBA), bare metal stenting, newer generation stenting and brachytherapy have established the

superiority of newer generation DES to other percutaneous coronary intervention (PCI) devices in treating ISR.³⁴⁻⁴⁸

In the last decade, paclitaxel drug-coated balloon catheters (DCBs) emerged as a competitive treatment option for ISR, as demonstrated in a large meta-analysis of 27 trials with a total of 5923 patients where paclitaxel DCB, among other ISR therapies (including POBA, debulking techniques, brachytherapy, BMS, DES), was the second most preferable approach to treating ISR but without a significant difference over limus therapies or paclitaxel-eluting stents.⁴⁹

Despite the large volume of published data, the superiority of the everolimus-eluting stents (EES) compared with DCB remains controversial, particularly as the meta-analysis discussed above suggests but also because DCBs are currently not available for use in the United States⁵¹ and no DCB coated with everolimus has been assessed to date to evaluated efficacy in treating ISR.

1.3 Study Rationale

Whereas the concerning long-term outcomes of paclitaxel-coated DCB catheters have led to controversy in the interventional vascular community⁵²⁻⁵⁶, CVT has developed a possible catheter-based treatment alternative by combining a proven percutaneous transluminal coronary angioplasty (PTCA) catheter, designed to treat in-stent restenosis in coronary arteries, with a drug-coating using a proven drug, everolimus. Everolimus is an active pharmaceutical agent with a proven history of safety and efficacy for use in coronary applications.

Everolimus [40-O-(2-hydroxyethyl)-rapamycin], is a semisynthetic macrolide immunosuppressant, which is in the same family as rapamycin (i.e., the "limus family of drugs") that inhibits mammalian target of rapamycin, and it is known to exert much higher interaction with rapamycin complex 2 leading to a blockage of protein synthesis. This interaction stops cell cycle progression, inhibits smooth muscle cell proliferation and reduces stent restenosis. In addition, everolimus has higher bioavailability and a shorter half-life than sirolimus, then it reduces vascular inflammation and stimulates rapid endothelialization¹.

Everolimus is a drug widely used in drug-eluting stents (DESs) and is considered as the percutaneous treatment of choice for coronary artery disease (CAD). The safety profile of everolimus-eluting stents is well established and the efficacy profile is greater than paclitaxel-eluting stents in long-term clinical follow-up².

Use of everolimus, a drug with an excellent safety profile and a proven history for cardiovascular use, with a proven PTCA catheter was demonstrated in series of preclinical evaluations in swine animal models. Extensive bench and pre-clinical studies demonstrated that the CVT Everolimus-coated PTCA Catheter is safe for its intended use with no adverse reactions associated to the drug delivery for the stented segment up to 30

¹ Trimukhe R, Vani P, Patel A, Salgotra V. Safety and performance of the EverProTM everolimus-eluting coronary stent system with biodegradable polymer in a real-world scenario. World J Cardiol. 2020;12(12):615-625. doi:10.4330/wjc.v12.i12.615

² Meng, M., Gao, B., Wang, X. et al. Long-term clinical outcomes of everolimus-eluting stent versus paclitaxel-eluting stent in patients undergoing percutaneous coronary interventions: a meta-analysis. BMC Cardiovasc Disord 16, 34 (2016). https://doi.org/10.1186/s1

days post-treatment in the animal model. The presence of everolimus in the vessel up to 30 days post-procedure, as demonstrated in pharmacokinetics studies, was associated with the possibility of prevention of restenostic reaction, characterized by signs of drug effects in the histopathology studies at that time point in the animal model.

The present trial will confirm the positive evaluations garnered to date of the CVT Everolimus- coated PTCA Catheter for its intended use of treating subjects with in-stent restenosis in native coronary arteries.

2. DESCRIPTION OF THE STUDY DEVICE

The Chansu Vascular Technologies (CVT) Everolimus-coated PTCA Catheter is a novel catheter designed to facilitate percutaneous treatment of subjects with in-stent restenosis in coronary arteries.

The CVT Everolimus-coated PTCA Catheter is comprised of two main components:

- 2.1 Basic Catheter Specifications

CONFIDENTIAL

Balloon Diameter (mm)	Balloon Length (mm) and Total Drug Content (µg)						
Nominal dose of everolimus:							

Table 1. CVT Everolimus-coated PTCA Catheter Size Matrix and Total Drug Content

2.2 Indication

The CVT Everolimus-coated PTCA Catheter is intended to be used for improving luminal diameter and myocardial perfusion in patients presenting in-stent stenotic lesions ≤24mm in length in native coronary arteries with reference vessel diameters of 2-3.5mm.

For additional information, refer to the Instructions for Use provided as Appendix E.

3. STUDY DESIGN

The CVT-ISR Trial investigates the inhibition of restenosis using the CVT Everolimus-coated PTCA Catheter in the treatment of in-stent stenotic lesions \leq 24 mm in native coronary arteries with reference vessel diameters of 2 to 3.5mm. The clinical study will be a prospective, multicenter, open, single-arm study.

Each subject will be followed for at least 3 years (36 months) after treatment. All subjects will have a follow-up contact or an optional office/hospital/clinic visit at 30 days. A follow-up office/hospital/clinical visit will occur at 6, 12, and a follow up phone call will occur at 24 and 36 months.

To participate in this study, the site will need the resources necessary for conventional vascular surgery as well as for fluoroscopy-guided catheter-based procedures with high quality imaging.

The study participation flow chart is provided in Figure 1.

Figure 1. CVT-ISR Study Participation Flow Chart

3.1 Endpoints

The definitions for the endpoints of this study are taken from the Academic Research Consortium-2 Consensus Document, Standardized End Point Definitions for Coronary Intervention Trials.³ Regarding the definition for Clinically Relevant Myocardial Infarction after Coronary Revascularization, this study adheres to the Expert Consensus Document from the Society for Cardiovascular Angiography and Interventions (SCAI)⁴, Consideration of a New Definition of Clinically Relevant Myocardial Infarction after Coronary Revascularization.

3.2 Primary Safety Endpoint

The primary safety endpoint for the study is freedom from target lesion failure (TLF) rate at 6 months post-index procedure, defined as a composite rate of: all cardiac death, target vessel myocardial infarction and clinically-driven target lesion revascularization (TLR).

3.3 Primary Effectiveness Endpoint

The primary effectiveness endpoint for the study is late lumen loss (LLL) at 180 days post procedure.

3.4 Other Clinical Endpoints

³ Garcia-Garcia HM, McFadden EP, Farb A, et al. Standardized End Point Definitions for Coronary Intervention Trials: The Academic Research Consortium-2 Consensus Document. Circulation. 2018;137(24):2635-2650. doi:10.1161/CIRCULATIONAHA.117.029289

⁴ Moussa ID, Klein LW, Shah B, et al. Consideration of a new definition of clinically relevant myocardial infarction after coronary revascularization: an expert consensus document from the Society for Cardiovascular Angiography and Interventions (SCAI). J Am Coll Cardiol. 2013;62(17):1563-1570. doi:10.1016/j.jacc.2013.08.720

- Target lesion failure (TLF) at 30 days, 1, 2 and 3 years, post-procedure, defined as a composite rate of cardiovascular death, target vessel myocardial infarction and clinically-driven target lesion revascularization (TLR).
- Target vessel failure (TVF) at 30 days, 180 days and 1, 2 and 3 years post-procedure, defined as a composite rate of cardiovascular death, target vessel myocardial infarction, and target vessel revascularization (TVR).
- Clinically-driven target lesion revascularization (TLR) at 1, 2 and 3 years post-procedure.
- Clinically-driven target vessel revascularization (TVR) at 180 days and 1, 2 and 3 years post-procedure.
- Rate of vascular access site complication, defined as the combined rate of hematoma, AV fistula or a pseudoaneurysm that required intervention, such as surgical repair or transfusion, prolonged hospital stay or required a new hospital admission.
- Lesion success (per device), defined as achievement of a final in-lesion residual diameter stenosis of <30% (by QCA), using any device after wire passage through the lesion. Pre- and post-dilatation of the lesion with a non-study device is considered part of assigned device treatment.
- Technical success (per device), defined as achievement of a final in-lesion residual diameter stenosis of <30% (by QCA), using the CVT Everolimus-coated PTCA Catheter without a device malfunction after wire passage through the lesion. Pre- and post-dilatation are considered part of assigned device treatment.
- Clinical success (per subject) defined as technical success without the occurrence of major adverse events during the procedure.
- Procedural success (per subject) defined as lesion success without the occurrence of major adverse events during the procedure.

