4.3 ISR PTCA Procedure

Procedural Medications

During the procedure, the subjects will receive appropriate anticoagulation and other therapy according to standard hospital practice. The use of any medication for the treatment of vessel spasm, subject agitation or discomfort, hypotension, arrhythmias and hemodynamic changes during the procedure is at the discretion of the investigator.

Treatment Strategy

The treatment strategy for all subjects enrolled in the clinical investigation is as follows:

- Treatment of a single in-stent restenosis lesion in a native coronary artery with up to two (2) CVT Everolimus-coated PTCA Catheters.
- Target lesion must be treated after meeting all the general and angiographic inclusion and exclusion criteria.
- Pre-dilation of target lesion is mandatory.
- Treatment of target lesion measuring ≤ 24 mm in length by visual estimation in vessel of visually estimated diameter ≥ 2.0 mm and ≤ 3.5 mm.
- Recommendation is to select a CVT EVE-PTCA Catheter with a balloon length that allows for coverage of the targeted lesion plus approximately 2 mm additional coverage, by visual estimate, on each side of the lesion while not allowing the balloon length extend beyond the edges of the stent.

PTCA Procedure

Vascular access should be obtained as per site standard of care (depending on lesion location, subject factors or any other factors that would impact the choice of vascular access).

Angiography must be conducted according to the angiographic core laboratory guidelines.

As a next step, a compatible sheath should be inserted and anticoagulation should be administered as per the Investigator's discretion to obtain or maintain appropriate clotting time (reference section 4.2. Concomitant Medical Therapy). In order to identify the anatomical characteristics of the vasculature and to visualize and define the lesion, selective angiography will be performed. Following angiography, the appropriate catheter size(s) will be selected.

Pre-dilatation will be performed on all subjects per the following sequence: after crossing of the target lesion with a guidewire, pre-dilatation is performed with a non-study balloon catheter, making sure that the balloon length is shorter than previously placed stent

length. Note that the use of a non-drug coated standard semi-compliant balloon or cutting/scoring balloon is allowed.

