6.4 Statistical Analyses

Detailed analyses of the primary endpoints will be performed when all of the subjects complete their primary follow-up visit at 180 days. No effort will be made to impute or extrapolate data to replace missing values. All calculations will be based on available data with missing data excluded.

Analysis of Primary Endpoints

The primary safety endpoint of freedom from target lesion failure (TLF) rate at 6 months post-index procedure will be analyzed using the safety population.

The analysis of the primary effectiveness endpoint of LLL at 6 months will utilize the evaluable populations.

Analysis of Secondary Endpoints

All secondary endpoints will be analyzed using descriptive statistics.

For binary variables, such as technical success counts, percentages and exact 95% confidence intervals using Clopper-Pearson's method will be calculated. For continuous variables, means, standard deviations, and 95% confidence intervals for the mean using the Gaussian approximation will be calculated. If the assumption of normality seems untenable, nonparametric methods will be employed instead.

For time-to-event variables, such as time to target lesion revascularization, survival curves will be constructed using Kaplan-Meier estimates.

Analysis of Other Data

The clinical laboratory values collected will be analyzed by tabulating the number and percentage of subjects with clinically significant changes from baseline for each parameter at each time point.

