11.4. Catheter Introduction and Dilatation

- 1. The CVT Everolimus-coated PTCA Catheter can be introduced percutaneously through an appropriately sized introducer sheath. *Do not attempt to use a smaller sized introducer sheath than indicated on the product label.*
- 2. Apply negative pressure to the balloon.

- 3. Place the prepared CVT Everolimus-coated PTCA Catheter over a pre-positioned guidewire, which has been placed through the lesion, and introduce the catheter percutaneously. Negative pressure should be maintained during advancement over the guidewire. Advance the catheter tip to the treatment location. A suitable length guidewire should be used at all times to maintain control and position of the guidewire.
- 4. Use fluoroscopic guidance for all further catheter manipulations during the procedure. If resistance is encountered at any time during the insertion procedure, do not force passage. Resistance may cause damage to the device or lumen. If resistance is encountered carefully withdraw the CVT Everolimus-coated PTCA Catheter. It may be necessary to remove the device, guidewire and guiding catheter/sheath as one unit.
- 5. Position the CVT Everolimus-coated PTCA Catheter at the treatment location. The radiopaque marker bands indicate the working length of the balloon. *The position of the balloon may only be modified with the guidewire in place.*
- 6. Inflate the balloon to dilate the desired target diameter according to the compliance chart printed on the device packaging. Inflation should be maintained for sixty (60) seconds. *Inflation should not be in excess of the rated burst pressure*.
- 7. Deflate the balloon and apply negative pressure.
- 8. With the guidewire in place and with negative pressure in the balloon, withdraw the CVT Everolimus-coated PTCA Catheter. *Do not retract the device unless the balloon is free and fully deflated.*
- 9. If more than one CVT Everolimus-coated PTCA Catheter is required to treat a single lesion, the balloon portion of each device must overlap by at least one (1) centimeter. A new, unused balloon must be used for each deployment. *No more than 2 devices can be used to treat a single lesion.*
- 10. Results should be verified by angiography.
- 11. The CVT Everolimus-coated PTCA Catheter is a single use device. Do not re-use or re-sterilize.
- 12. If the CVT Everolimus-coated PTCA Catheter has entered the vasculature and cannot be deployed, the device CANNOT be re-inserted for deployment.

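### Lesion success is labelled per device but is one outcome per lesion, so taken literally a lesion treated with two balloons enters the analysis twice

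*Combined protocol and SAP*

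**What the plan says.** Section 3.4 of the protocol gives four acute success endpoints, and the Protocol Summary uses the same units.

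- Lesion success: "Lesion success (per device), defined as achievement of a final in-lesion residual diameter stenosis of <30% (by QCA), using any device".
- Technical success is also labelled per device. It uses the same stenosis criterion, reached with the study catheter and without a device malfunction.
- "Clinical success (per subject) defined as technical success", with no major adverse event during the procedure.
- "Procedural success (per subject) defined as lesion success without the occurrence of major adverse events during the procedure".

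Section 4.3 sets the treatment as "Treatment of a single in-stent restenosis lesion in a native coronary artery with up to two (2) CVT Everolimus-coated PTCA Catheters". The Instructions for Use (Appendix E, section 11.4) repeat the limit: "No more than 2 devices can be used to treat a single lesion". The Protocol Summary states: "A total of 50 subjects will be enrolled".

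Section 6.4 makes all secondary endpoints descriptive. For binary variables, with technical success as its example, it plans "exact 95% confidence intervals using Clopper-Pearson's method". It states no denominator and no allowance for two records from one lesion.

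In Appendix L, a second balloon calls for a second Procedural Form. That form has an item for the target lesion's final percent stenosis once all treatment is complete.

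**The concern.** A final in-lesion stenosis reached with any device is a property of the lesion. It has one value however many balloons were used. If the stated unit is followed, a lesion treated with two balloons contributes two records that must agree.

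This has two consequences. The success rate becomes a weighted mean in which two-balloon lesions count double, so it can move if those lesions do better or worse than the rest. And Clopper-Pearson assumes independent trials, while two records of one stenosis are fully dependent.

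The stenosis part of technical success has the same problem. Its malfunction part is a true device-level outcome. The units also do not join up: clinical and procedural success are per subject but are built on per-device endpoints, and no rule converts one to the other. If one of two balloons malfunctions, the plan does not say whether the subject is a technical success.

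**Working it through.** **Inputs.** There are 50 subjects with one target lesion each (Protocol Summary; sections 3.6 and 4.3), and one or two study balloons per lesion (section 4.3; Appendix E, section 11.4). The interval is Clopper-Pearson at 95% (section 6.4). Two inputs are assumptions because the documents do not give them: the number m of two-balloon lesions (possible range 0 to 50) and the true success rate p (80% to 98% examined).

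**Check of the method.** Section 6.3 gives a 90% interval of 73% to 92% for 42 of 50 subjects. Clopper-Pearson gives 73.0% to 91.8%, so the plan's figure is reproduced. It uses a per-subject count. The plan gives no figure for lesion success.

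**Point estimate.** Take 5 failed lesions of 50 and m = 10, which makes 60 device records.

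- Per lesion: 45/50 = 90.0%.
- Per device, no failure in a two-balloon lesion: (60 - 5)/60 = 55/60 = 91.7%.
- Per device, one failure in a two-balloon lesion (the same failure share in both groups): (60 - 6)/60 = 54/60 = 90.0%.
- Per device, all five failures in two-balloon lesions: (60 - 10)/60 = 50/60 = 83.3%.

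**Interval width, 95% Clopper-Pearson.**

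| Count | Interval | Width (points) |
|---|---|---|
| 45/50 (per lesion) | 78.2% to 96.7% | 18.5 |
| 55/60 | 81.6% to 97.2% | 15.6 |
| 54/60 | 79.5% to 96.2% | 16.7 |
| 50/60 | 71.5% to 91.7% | 20.2 |

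The per-device interval is often narrower, but 50/60 is wider than 45/50.

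**Information in the duplicated data.** With weights of 1 and 2, the design effect is (50 - m + 4m)/(50 - m + 2m) = (50 + 3m)/(50 + m). For m = 10 it is 80/60 = 1.33, so 60 records carry the information of 60/1.33 = 45 independent ones. For m = 50 it is 200/100 = 2.00, which gives 50. The effective number never exceeds the 50 lesions.

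**Coverage.** Let i of the 50 - m one-balloon lesions and j of the m two-balloon lesions succeed. The device count is i + 2j of 50 + m. Coverage is the sum of Bin(i; 50 - m, p) × Bin(j; m, p) over all pairs whose interval contains p. Coverage of the nominal 95% interval, in percent:

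| m | p = 80% | 84% | 85% | 90% | 95% | 97% | 98% |
|---|---|---|---|---|---|---|---|
| 0 | 96.7 | 96.9 | 97.3 | 97.0 | 98.8 | 98.3 | 98.2 |
| 10 | 93.4 | 93.6 | 94.2 | 94.2 | 97.8 | 97.8 | 98.2 |
| 20 | 90.4 | 88.2 | 91.8 | 88.8 | 94.5 | 95.2 | 96.3 |

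Exact coverage moves in steps between these rates. With m = 10 on a half-point grid, the same sum runs from 91.7% to 95.6% for p between 80% and 90%, and from 96.4% to 98.2% for p between 95% and 98%. At the extreme, m = 50, coverage is 82.6% at p = 84%, 83.0% at 90% and 88.5% at 95%.

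**The case against.** Several points on the other side stand.

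- **The denominator is never written out.** Double counting follows from the per-device label, and a reader might infer that it is an explicit instruction. The wording about any device, with pre- and post-dilatation counted as part of treatment, also fits one outcome per lesion. But per device is the only unit the plan states for this endpoint, and no other section corrects it.
- **The Procedural Form does not settle it.** The endpoint is by QCA, which Appendix B assigns to the angiographic core laboratory. The form's final-stenosis item is not identified as QCA. A second site form does not show that the core laboratory value would be entered twice, so the point rests on section 3.4.
- **The interval is not always too narrow, and coverage is not always below 95%.** Both stronger readings are tempting, and both fail. 50/60 gives a wider interval than 45/50. Clopper-Pearson is conservative, so moderate duplication at high success leaves coverage above 95%. High success is plausible, because section 4.3 requires residual stenosis below 30% by visual estimate after pre-dilatation, although QCA may read differently.
- **The number of two-balloon lesions is unknown.** Balloon sizes are not shown in the public Table 1, so how often two are needed cannot be judged.
- **A device unit is partly right for technical success**, because malfunction belongs to the device.

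None of this supplies a reason to count one final stenosis twice.

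**Conclusion.** The point holds in conditional form. The stated unit does not match the outcome. If it is followed, two-balloon lesions are over-weighted and their duplicate results are treated as independent.

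The size rests on an assumed number of two-balloon lesions:

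- None: no effect.
- 10 of 50: coverage about 93-94% at the tabulated true success rates from 80% to 90%, and above 95% from 95% to 98%. With 5 failed lesions, the reported rate could lie anywhere from 83.3% to 91.7% instead of 90.0%.
- 20 of 50: coverage about 88-92% at the tabulated rates from 80% to 90%, and about nominal from 95% to 98%.

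A reader might infer that the trial's main conclusions are at risk. They are not. These endpoints are descriptive under section 6.4, and the two primary endpoints and the sample size do not use them. This is a minor correction, worth making before the data are seen because otherwise the analyst must either follow the label or choose a denominator afterwards.

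**What to change.** In the Protocol Summary and section 3.4:

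1. Define lesion success per lesion, which here equals per subject, with one final QCA value and one entry per treated subject.
2. Define technical success once per subject for use in clinical success, and state how a malfunction of one of two balloons counts.
3. Keep a per-device denominator only for device malfunction.

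The cost is endpoint wording. No extra data, visits or subjects are needed. The reported interval will usually be slightly wider, for example 18.5 points (45/50) in place of 16.7 (54/60).
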